**PROTOCOL COVER PAGE**

**REVISION HISTORY**

Revision #	Version Date	Summary of Changes	Consent Change?
3	5/9/19	Adjusted inclusion criteria to include those who are not enrolled in the TSA study.	

**ABBREVIATIONS/DEFINITIONS**

- LB liposome bupivacaine
- ISB interscalene block
- TSA total shoulder arthroplasty
- RCR rotator cuff surgery

## 2.0 Objectives

- 2.1 Purpose: To evaluate the movement of the diaphragm after an interscalene block with liposome bupivacaine (LB) compared to interscalene block (IB) with bupivacaine. **This study will evaluate if there is a possible prolonged phrenic nerve paralysis when using liposome bupivacaine in an interscalene block, using ultrasound.**

## 3.0 Background

- 3.1 Significance of Research Question/Purpose: To date there is no previous study looking at diaphragm movement after an Liposomal Bupivacaine Interscalene Block. It is important to see how long the phrenic nerve is affected by this block if at all.
- 3.2 Preliminary Data: We have not routinely examined that patient's diaphragm via ultrasound after ISB at M Health. Patients have not been readmitted for breathing problems with our current practice.
- 3.3 Existing Literature: There is no previous literature in LB ISB. Urmev et al. showed 100% phrenic nerve block post ISB. But others (Renes et al) have evaluated it using bupivacaine and found that lower doses resulted in less diaphragm blockade. Cuvillon showed that those with a catheter had 66% phrenic nerve paralysis at 24 hours.

## 4.0 Study Endpoints/Events/Outcomes

- 4.1 Primary Endpoint/Event/Outcome: The primary study endpoint will be diaphragm excursion (movement in cm) from rest to sigh in a sitting position.
- 4.2 Secondary Endpoint(s)/Event(s)/Outcome(s): The secondary endpoint will be the diaphragm excursion (movement in cm) from rest to a quick inspiratory breath.
- 4.3 Secondary Endpoint(s)/Event(s)/Outcome(s): Evaluation of baseline FEV1, FVC (or FEV6) and FEV1/FVC ratio via spirometry.

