## 5.0 Study Intervention(s)/Investigational Agent(s)

- 5.1 Description: This study will be run concurrently with two other studies comparing bupivacaine to Liposomal Bupivacaine in shoulder surgeries. We will either use already randomized patients for our randomization process or if they are not enrolled in either RCR or TSA study we will randomize them to one of the two groups. For this study in particular we will use an ultrasound machine to scan the diaphragm of any patient who had an Interscalene Block for Total Shoulder Arthroplasty or Rotator Cuff Repair. Patients are to be scanned in an upright sitting position and scanned from a low intercostal or subcostal approach using the liver or spleen as an acoustic window. M Mode will be applied and the range of diaphragmatic movement from the resting expiratory position to deep inspiration (sigh test) will be

recorded as was the range of diaphragmatic movement from resting expiratory position when quickly inspiring through the nose (sniff test). The blocks will be done regardless of the study as they are standard of care for pain control. The only intervention is ultrasound examination of the patient's diaphragm at baseline, 3 hours post block in recovery room and on post-operative day 1, and basic spirometry to record FEV1 and FVC via a portable spirometer at the same time points. If patients did stay in hospital on postoperative day 2 we would also evaluate their diaphragm function.

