5.2 Drug/Device Handling: n/a

5.3 Biosafety: n/a

5.4 Stem Cells: n/a

## 6.0 Procedures Involved

6.1 Study Design: This is a prospective study

Study Procedures: All patients who are enrolled in our TSA or RCR studies fit the criteria of being scheduled for overnight shoulder surgery and having an ISB with or without LB. The patients will already be randomized into either an ISB with bupivacaine or with bupivacaine and LB. If the patient is not enrolled or does not fit inclusion criteria for the RCR or TSA study they will then be randomized to either bupivacaine or liposome bupivacaine ISB. The patients will perform spirometry (one large exhale into a spirometer) and have an ultrasound examination of their diaphragm at baseline prior to the block, in PACU after their procedure, and on postoperative day 1 (24 hours after ISB). Diaphragmatic movement will be evaluated by real-time M-mode ultrasonography of the hemidiaphragm using a 17-mm 1- to 5-MHz broadband phased array US probe. Patients are to be scanned in an upright sitting position and scanned from a low intercostal or subcostal approach using the liver or spleen as an acoustic window. M Mode will be applied and the range of diaphragmatic movement from the resting expiratory position to deep inspiration (sigh test) will be recorded as well as the range of diaphragmatic movement from resting expiratory position when quickly inspiring through the nose (sniff test). This will occur three times, at baseline prior to surgery, in the recovery room, and on the ward on postoperative day 1. All nerve blocks will be confirmed to be functional via a sensory skin test prior to surgery or in the recovery room prior to the recovery room evaluation.

6.2 Study Duration: The patients will be in the study for 2 days. The duration of the study should be 3 months to enroll the 22 patients.

6.3 Individually Identifiable Health Information: PHI will be recorded but once data collection is done then the phi will be removed and replaced with unique identifier. This is just to ensure we see the correct patient for the data collection.

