6.4 Use of radiation: n/a

6.5 Use of Center for Magnetic Resonance Research: n/a

## 7.0 Data and Specimen Banking

- 7.1 Storage and Access: the data will be kept in the University box. Data is kept for 7 years.
- 7.2 Data: The data kept will be patient demographics such as weight, BMI, age, sex. Also, block medications and volume used, time of injection, surgical procedure, range of diaphragm movement at baseline, in recovery room, and on postoperative day 1 and spirometry at baseline, in recovery and postoperative day 1.
- 7.3 Release/Sharing: data will be kept with the PI and co-I

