### **15.0 Statistical Considerations**

15.1 Data Analysis Plan: We will use the average of the three US exams for each timed measurement as the definitive measurement. We will also use FEV1, FVC (or FEV6) and FEV1/FVC (or FEV6) ratio for each time period as a secondary measurement. This data will be given to the statistician who will compare those in the LB ISB group to the bupivacaine ISB group to evaluate for differences (if any) between the movement of the diaphragms in each group.

*15.2* Power Analysis: We assumed a 5% rate of block at 24 hours in bupivacaine and a 66% block for liposome bupivacaine. With an alpha of 0.05 and power of 80% we determined we need 9 patients in each group. Assuming we would have 20% patients drop out, screen fail, or discharge early we planned to enroll 11 per group for total of 22 patients.

*15.3* Statistical Analysis: This study will be analyzed by our staff biostatistician. The data will be de-identified and shared with him in box. The statistician will be provided the protocol so they are able to analyze for primary and secondary objectives.

*15.4* Data Integrity: All patients will be assigned a unique patient identifier. The data that will be sent to the statistician will be de-identified.

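### Section 4.3 lists only pre-block spirometry as the secondary endpoint, and no section states a baseline-adjusted comparison of the post-block values

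*Combined protocol and SAP*

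**What the plan says.** - **Section 4.3** lists the spirometry secondary endpoint as "Evaluation of baseline FEV1, FVC (or FEV6) and FEV1/FVC ratio via spirometry". It names no time after the block.
- **Section 6.1 (Study Procedures)** schedules spirometry and ultrasound "at baseline prior to the block, in PACU after their procedure, and on postoperative day 1 (24 hours after ISB", so baseline is a pre-treatment value.
- **Section 5.1** adds to the ultrasound examinations "basic spirometry to record FEV1 and FVC via a portable spirometer at the same time points".
- **Section 7.2** keeps "spirometry at baseline, in recovery and postoperative day 1".
- **Section 15.1** states: "We will also use FEV1, FVC (or FEV6) and FEV1/FVC (or FEV6) ratio for each time period as a secondary measurement". The sentence that describes the comparison of the two groups names only diaphragm movement.
- **Section 15.2** bases the sample size on the rate of block at 24 hours.
- **Section 15.3** says: "The statistician will be provided the protocol so they are able to analyze for primary and secondary objectives".

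**The concern.** An endpoint in a comparison of two blocks has to be something the blocks can change. A value taken before either block is given does not meet that test. Its expected difference between randomised arms is zero, and any difference seen is chance.

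The statistician is sent to the protocol for the objectives. Section 4.3 there gives a pre-treatment time point. Section 15.1 gives all time points without saying which one matters or how baseline enters the comparison. Three measures at three times make nine possible between-arm comparisons. Three of these are baseline comparisons with no treatment content, and the other six are left open to choice after the data are seen.

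What is at stake is the one listed endpoint that does not come from ultrasound. In a trial of this size, chance imbalance in lung function before the block can be large, and an unadjusted comparison carries part of it into the result.

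**Working it through.** **1. The plan's own figure.** Section 15.2 assumes block rates of 5% and 66%, alpha 0.05 and power 80%. The two-sided normal formula with pooled variance and no continuity correction, with mean rate (0.05 + 0.66)/2 = 0.355, gives

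n = [1.96 × √(2 × 0.355 × 0.645) + 0.842 × √(0.05 × 0.95 + 0.66 × 0.34)]² / 0.61² = (1.326 + 0.439)² / 0.372 = 8.4, rounded up to 9 per group.

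The stated 9 is reproduced. It rests on the 24-hour block rate and not on spirometry, so nothing below changes it.

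**2. Sections side by side.**

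| Section | Baseline | Recovery room | Postoperative day 1 |
|---|---|---|---|
| 4.3 (endpoint) | yes | not named | not named |
| 5.1 (intervention) | yes | yes | yes |
| 6.1 (procedures) | yes | yes | yes |
| 7.2 (data kept) | yes | yes | yes |
| 15.1 (analysis) | each time period | each time period | each time period |

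Only 4.3 is out of line. No section states a key time point, a summary measure or a baseline adjustment for spirometry.

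**3. A comparison at baseline.** The true difference is zero by randomisation, so a two-sided 5% test rejects 5% of the time whatever the blocks do. A simulation with 9 per group and normal data gave 4.99%.

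**4. Chance imbalance at baseline.** With 9 per group, the difference in baseline means has standard error √(2/9) = 0.47 SD. The probability of an imbalance beyond 0.5 SD in either direction is P(|Z| > 0.5/0.471 = 1.06), about 29%. An unadjusted post-block comparison carries on average r × imbalance into the result, where r is the correlation between baseline and post-block values. For an imbalance of 0.5 SD that is 0.5 × 0.5 = 0.25 SD at r = 0.5 and 0.7 × 0.5 = 0.35 SD at r = 0.7.

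**5. Gain from adjustment.** The documents give no value for r; 0.5 to 0.7 is assumed.

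- Large samples: residual variance is multiplied by 1 − r². At r = 0.5 this is 0.75, a 25% cut. At r = 0.7 it is 0.51, a 49% cut.
- With 18 patients in two groups, estimating the slope costs a factor of 1 + 1/14 = 1.071. At r = 0.5, 0.75 × 1.071 = 0.80, a cut of about 20%. At r = 0.7, 0.51 × 1.071 = 0.55, a cut of about 45%.
- Break-even: adjustment helps on average when (1 − r²) × 15/14 < 1, that is r² > 1/15, or r above about 0.26.

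**The case against.** The strongest reply is that the protocol should be read as a whole. Post-block spirometry is scheduled in 5.1 and 6.1, kept under 7.2 and named for use in 15.1. Section 15.3 gives the statistician the whole protocol and does not say that Section 4 overrides 15.1. On that reading, the word baseline in 4.3 is a drafting slip. This stands. A reader might infer from 4.3 that the plan cannot say anything about lung function after the block, and the documents do not support that.

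It is also fair that 15.1 prescribes no between-arm test of baseline spirometry. Its reference to each time period fits equally well with baseline as a reference value. Nor does it prescribe an unadjusted comparison, although a comparison by time period is its plainest reading. The accurate criticism is that the analysis is not specified.

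Sections 4.1 and 4.2 name no time point either, so that gap is not peculiar to spirometry. What is peculiar to 4.3 is that it names a time point, and it is one before treatment.

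A reader might go further and infer from "one large exhale into a spirometer" that the measurement is inadequate because ultrasound is averaged over three examinations, or that allowing FEV6 in place of FVC undermines the endpoint. Nothing in the documents shows either. These are measurement choices and do not follow from the conflict described here.

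The reply does not supply the missing comparison. Collecting and storing values at three times does not say which contrast is the endpoint or how baseline is used.

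**Conclusion.** The point holds in a limited form. Section 4.3 lists a pre-treatment value as a secondary endpoint, which conflicts with 5.1, 6.1, 7.2 and 15.1, and no section states a baseline-adjusted post-block comparison. It concerns one secondary endpoint. The post-block data will exist, so the defect lies in specification and not in collection.

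The gain from adjustment is a cut of about 20% to 45% in residual variance with 9 per group. This assumes a correlation of 0.5 to 0.7, a linear relation, similar variance in the two arms and 18 analysable patients. If the block weakens the correlation, the gain shrinks, and it disappears on average below r of about 0.26.

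**What to change.** - **Section 4.3:** replace the baseline endpoint with post-block FEV1, FVC and FEV1/FVC. Name 24 hours after the block as the key time point, to match the time point used in 15.2, with the recovery-room values also reported.
- **Section 15.1:** state that arms are compared on the post-block spirometry values with adjustment for each patient's own baseline value, for example by analysis of covariance. State that baseline serves only as a covariate and is not tested between arms as an outcome.

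The cost is one line in each of two sections. The baseline reading is already collected, so there is no extra measurement, visit or patient. One degree of freedom goes to the covariate, which the small-sample figures above already allow for.

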## 5.0 Study Intervention(s)/Investigational Agent(s)

- 5.1 Description: This study will be run concurrently with two other studies comparing bupivacaine to Liposomal Bupivacaine in shoulder surgeries. We will either use already randomized patients for our randomization process or if they are not enrolled in either RCR or TSA study we will randomize them to one of the two groups. For this study in particular we will use an ultrasound machine to scan the diaphragm of any patient who had an Interscalene Block for Total Shoulder Arthroplasty or Rotator Cuff Repair. Patients are to be scanned in an upright sitting position and scanned from a low intercostal or subcostal approach using the liver or spleen as an acoustic window. M Mode will be applied and the range of diaphragmatic movement from the resting expiratory position to deep inspiration (sigh test) will be

recorded as was the range of diaphragmatic movement from resting expiratory position when quickly inspiring through the nose (sniff test). The blocks will be done regardless of the study as they are standard of care for pain control. The only intervention is ultrasound examination of the patient's diaphragm at baseline, 3 hours post block in recovery room and on post-operative day 1, and basic spirometry to record FEV1 and FVC via a portable spirometer at the same time points. If patients did stay in hospital on postoperative day 2 we would also evaluate their diaphragm function.

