## **9.0 Study Population**

- 9.1 Inclusion Criteria: All patients age 18 years and older who are scheduled for shoulder surgery with interscalene block and remain in the hospital for more than 24 hours that are being randomized into a bupivacaine versus LB ISB block study or those who are not enrolled in the TSA or RCR study but are having shoulder surgery with ISB and planned to spend one night in the hospital.
- 9.2 Exclusion Criteria: Non-English speaking patients.
- 9.3 Screening: On the week to day prior to surgery patients will be identified from surgical case list. Then prior to or on day of surgery patients will be asked to participate in the study and given enough time to decide to participate and ask questions.

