**12.0 Local Recruitment Methods**

*12.1 Recruitment Process:* No recruitment posters. Only recruit from surgical lists. Patients will be recruited from the group of adult surgical patients at the University of Minnesota undergoing shoulder surgery and receiving an interscalene block scheduled for overnight stay that elected to participate in another ISB bupivacaine versus LB shoulder study. Patients will be approached at the preoperative assessment clinic or surgeon's clinic at the Clinic and Surgery Center if possible by a research staff member to determine their interest in participation. If they decide to be a participant they will be consented and given a copy of their consent form for their records and a consent will be scanned and placed into EPIC. These patients will have significant time to review the study with research staff as well as the physicians performing the procedure due to the fact they arrive several hours prior to their scheduled surgery. All subjects will have enough time to ask questions about the study and the potential risks involved regardless of which venue they are consented.

*12.2 Identification of Potential Participants:* Patients will be identified by members of the treatment team in either the surgeon's clinic, pre-assessment clinic, or preoperative area. Patients who have opted out of research will not be asked to participate in the study. Patients will be approached to consent for the study by a surgeon, anesthesiologist, or member of the research team. Patients who agree to participate in the study will sign both a study

consent and HIPAA authorization allowing the use of specified information contained in medical records for research purposes.

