## **19.0 Consent Process**

*19.1 Consent Process (when consent will be obtained):*

*Patients will be identified in the pre-operative time period by the block anesthesiologist or research team and if possible will be consented by the research coordinator or research assistant. If patients have more questions and do not want to sign at their clinic will be asked if it is allowable for a study staff member to contact them prior to surgery via phone to clarify if they have any questions. On the day of surgery, if the patient has not already signed consent and is still interested in participating in the study will be presented with consent and Health and Insurance Portability and Accountability Act (HIPAA) forms. The patient will review the forms with the research staff, or anesthesiologist. Subjects will be reminded that participation is completely voluntary, and that they may stop participation at any time without question or penalty. The research staff or anesthesiologist will answer any questions that the subjects may have*

*about the study. If the patient decides to participate, they will be asked to sign the consent and HIPAA forms. One copy will be saved for study records, and the subject will be provided with a copy of the forms for their own records. Waiver or Alteration of Consent Process (when consent will not be obtained):*

Non-English Speaking Participants: n/a.

19.2 Participants Who Are Not Yet Adults (infants, children, teenagers under 18 years of age):

- n/a

19.3 Cognitively Impaired Adults, or adults with fluctuating or diminished capacity to consent:

- n/a

19.4 Adults Unable to Consent:

- Permission: n/a
- Assent: n/a
- Dissent: n/a

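### Parent-study patients can enter after their block has been allocated, and nothing requires those who invite, consent, withdraw or scan them to be unaware of the arm

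*Combined protocol and SAP*

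**What the plan says.** Two routes lead into the study. On the first, the patient is already in one of two other trials of the same comparison, and that trial's allocation is used: "We will either use already randomized patients for our randomization process" (section 5.1) and "The patients will already be randomized into either an ISB with bupivacaine or with bupivacaine and LB" (section 6.1). Section 12.1 describes the recruitment pool as patients "that elected to participate in another ISB bupivacaine versus LB shoulder study". On the second route, for patients outside those trials, "they will then be randomized to either bupivacaine or liposome bupivacaine ISB" (section 6.1). No sequence, ratio or concealment is described for this second route.

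Consent to this study is a separate step. Section 9.3 says that "prior to or on day of surgery patients will be asked to participate in the study", and section 19.1 also allows signature on the day of surgery. Section 19.1 states: "Patients will be identified in the pre-operative time period by the block anesthesiologist or research team". Section 12.2 adds: "Patients will be approached to consent for the study by a surgeon, anesthesiologist, or member of the research team".

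Section 13.1 lets the surgeon withdraw a patient before surgery on any medical ground. Section 13.2 records those withdrawn before the procedure as screen failures. Section 6.1 places the baseline scan and spirometry before the block, without tying them to when the allocation becomes known.

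**The concern.** Randomisation protects a comparison of the people who were randomised. It does not automatically protect a subset assembled afterwards. If those who decide whom to invite, consent or withdraw know the arm, their decisions can differ by arm, and the two groups may then differ before any block is given.

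The study asks whether liposome bupivacaine prolongs phrenic nerve paralysis, so respiratory reserve is an obvious thing for a clinician to weigh. The only exclusion criterion concerns language, which leaves that judgement to discretion. A withdrawal filed as a screen failure would not be visible as a loss after allocation. The baseline sigh, sniff and spirometry all depend on effort, so a patient or scanner who knows the arm could also influence the measurement against which recovery is judged. Selective entry cannot be reliably undone in the analysis.

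**Working it through.** **1. Order of allocation and entry.** Sections 5.1 and 6.1 describe parent-study patients as randomised already, and section 12.1 recruits from people who have joined a parent trial. Section 9.1 speaks of patients in the course of being randomised, which leaves the order open. No section requires consent here to come before parent allocation. Entry after allocation is therefore permitted, and is the plainer reading of 5.1 and 6.1.

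**2. Who acts between allocation and block.**
- Identification: includes the block anesthesiologist (19.1).
- Consent: surgeon, anesthesiologist or research team (12.2), up to the day of surgery (9.3, 19.1).
- Withdrawal before surgery: surgeon (13.1), recorded as a screen failure (13.2).
- Baseline scan and spirometry: before the block (6.1).

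**3. Safeguards.** The document contains no statement on blinding, on allocation concealment, or on keeping recruiters or scanners unaware of the arm. It does not require every eligible parent-study patient to be approached, nor a log by arm.

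**4. The plan's own sample size.** Section 15.2 gives 5% and 66%, alpha 0.05, power 80%, 9 per group. With the two-sided pooled normal formula and no continuity correction, the mean proportion is 0.355, and

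n = [1.960 × √(2 × 0.355 × 0.645) + 0.842 × √(0.05 × 0.95 + 0.66 × 0.34)]² / 0.61² = (1.326 + 0.439)² / 0.3721 ≈ 8.4, rounded up to 9.

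This reproduces the stated figure, and 9 per arm is used below.

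**5. Hypothetical effect on the error rate.** Assume no true effect, a two-sided 5% t test on excursion, 9 per arm, and an entry imbalance of d standard deviations carried unadjusted into the comparison. The values of d are assumptions; the document gives no SD and no basis for d. The test has 16 degrees of freedom, critical value 2.120 and noncentrality d × √(9/2).

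| Assumed d | Noncentrality | Rejection rate |
|---|---|---|
| 0 | 0 | 5.0% |
| 0.25 | 0.530 | 7.9% |
| 0.5 | 1.061 | 17.0% |

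**6. A second illustration, from a selection model.** Take 11 per arm and no true effect. In one arm only, let entry depend on a standardised prognostic factor (5,000 simulations).

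| Log-odds slope per SD | Spurious difference (SD) | Rejection rate |
|---|---|---|
| 0 | 0.00 | 4.6% |
| 0.25 | 0.11 | 5.8% |
| 0.5 | 0.21 | 6.9% |
| 1.0 | 0.37 | 13.9% |

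Mild selection costs little. The 17% figure corresponds to stronger selection than any case in this second table.

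**The case against.** The strongest reply is that bias needs someone to know the arm, and the document never says that anyone does. Masking would be described in the parent protocols, which are not available here. If recruiters, patients and those deciding on withdrawal do not know the allocation, late entry alone causes no bias. This stands. A reader might infer that recruiters do know the arm and that randomisation has been lost; the document does not support that. It shows only that no safeguard is stated.

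Three further points carry some weight.
- Section 19.1 prefers consent by a coordinator or research assistant where possible, and section 12.1 similarly has research staff make the approach in clinic. This lowers the risk but leaves the other routes open.
- For parent-study patients, joining does not change the block; section 5.1 says that the study adds only ultrasound and spirometry. The motive to select at invitation is therefore weaker than in an ordinary trial. Withdrawal under 13.1 is the more concrete route.
- Baseline excursion is recorded, so an imbalance in it could be seen and adjusted for. Section 15.1 specifies no adjustment, however. Adjustment would not deal with unmeasured differences, or with a baseline itself affected by knowledge of the arm.

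A reader might also take the fall from 40 consented to 22 enrolled (section 11.1) as a measure of selection. It is not: it would be loss after consent, not selection at invitation, and the Resources Available section describes the same 40 as screened. Finally, patients randomised directly by this study would dilute an imbalance confined to the parent-study route.

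**Conclusion.** The point holds in conditional form. As written, the plan permits parent-study patients to be invited, consented, withdrawn and scanned at baseline after their arm has been set, by people not required to be unaware of it. If the parent allocation is not concealed from them, entry can depend on arm. Whether it is concealed is not shown, so confidence is medium.

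The size is unknown. The figures of about 8% to 17% are hypothetical and rest wholly on an assumed 0.25 to 0.5 SD imbalance affecting the whole sample, with no adjustment; the selection model gives about 6% to 14% for slopes of 0.25 to 1.0. The change should be made because selection cannot be reliably repaired after enrolment and prevention is cheap.

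**What to change.** Add to sections 9.3, 13.1 and 19.1:
- Invitation and consent are done by an existing team member who does not know the parent-study allocation, or before that allocation is made.
- Every eligible parent-study patient is approached.
- Refusals and pre-surgery withdrawals are logged by arm and by source (rotator cuff study, total shoulder study, directly randomised), with the arm filled in afterwards. A withdrawal after allocation then remains visible even where it is classed as a screen failure.
- The baseline scan and spirometry are completed before the allocation is opened to the patient or the person scanning.
- For directly randomised patients, the assignment stays concealed until consent and baseline are complete.

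This needs a few sentences, a log and some reordering of existing steps, with no added patients or visits. The downside is that some invitations must pass to another existing team member. Using a recruiter unaware of the arm can be arranged within this protocol; tying consent to the moment of parent randomisation could require amendments to two other protocols, so the first option is the easier one. The surgeon's discretion to withdraw a patient is unchanged.
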